11.8 Financial Disclosure

Investigators are required to provide financial disclosure information to the Sponsor to permit the Sponsor to fulfill its obligations under 21 CFR Part 54. In addition, Investigators must commit to promptly updating this information if any relevant changes occur during the study and for a period of 1 year after the completion of the study.

12 STUDY ADMINISTRATIVE INFORMATION

12.1 Protocol Amendments

[figure not shown]
Any amendments to the study protocol will be communicated to the Investigators by [REDACTED] or the Sponsor. All protocol amendments will undergo the same review and approval process as the original protocol. A protocol amendment may be implemented after it has been approved by the IRB, unless immediate implementation of the change is necessary for subject safety. In this case, the situation must be documented and reported to the IRB within 5 working days.

13

[figure not shown]
REFERENCES

[figure not shown]
The image consists of a black background with several horizontal white bars of varying lengths. These bars are arranged in a staggered, non-overlapping pattern. On the far left edge, there is a vertical column of small, white, square-like marks, possibly representing a frame border or a specific data visualization element. The bars themselves are relatively thin and have sharp edges.

APPENDIX A: SCHEDULE OF PROCEDURES

Appendix A: SCHEDULE OF PROCEDURES (Continued)

APPENDIX B: CLINICAL LABORATORY ANALYTES

Standard Safety Chemistry Panel

Alanine aminotransferase	Albumin
Alkaline phosphatase	Amylase
Aspartate aminotransferase	Bicarbonate
Blood urea nitrogen	Calcium
Chloride	Creatine kinase
Creatinine	Direct bilirubin
Estimated glomerular filtration rate	Gamma-glutamyl transferase
Glucose	Indirect bilirubin
Inorganic phosphorus	Lactate dehydrogenase
Lipase	Potassium
Sodium	Total bilirubin
Total protein	Uric acid

Endocrinology

Follicle-stimulating hormone (FSH) [1]

1. An FSH test will be performed at Screening in all naturally postmenopausal women to confirm menopausal status.

Hematology

Hematocrit	Hemoglobin
Platelets	Red blood cell count

White blood cell count and differential [1]

1. Manual microscopic review is performed only if white blood cell count and/or differential values are out of reference range.

Urinalysis

Bilirubin	Blood
Glucose	Ketones
Leukocyte esterase	Microscopy [1]
Nitrite	pH
Protein	Specific gravity

Urobilinogen

1. Microscopy is performed only as needed based on positive dipstick test results.

Pregnancy Tests

Serum human chorionic gonadotropin [1] Urine human chorionic gonadotropin [2]

1. A serum pregnancy test will be performed in all females of childbearing potential at Screening.
2. A urine pregnancy test will be performed in all females of childbearing potential at Check-In (both treatment periods).

Viral Serology

Hepatitis B virus surface antigen
Human immunodeficiency virus antibody

Hepatitis C virus antibody
Severe acute respiratory syndrome
coronavirus-2 RNA

Urine Drug Screen

3,4-methylenedioxymethamphetamine
Barbiturates
Cannabinoids
Cotinine
Methamphetamine
Oxycodone
Tricyclic antidepressants

Amphetamines
Benzodiazepines
Cocaine
Methadone
Opioids
Phencyclidine

Lipid Panel

[figure not shown]
High-density lipoprotein cholesterol
Total cholesterol

Low-density lipoprotein cholesterol
Triglycerides

Other Tests

Blood phosphatidyl ethanol
Blood ethanol

APPENDIX C: SYMPTOM ASSESSMENT SCALES

Alcohol Toxicity Symptom Scale

1 INTRODUCTION

The purpose of this Statistical Analysis Plan (SAP) is to provide a description of the statistical methods to be implemented for the analysis of data from the study with protocol number ADX-629-ET-001, version 3.0. The SAP will be finalized prior to database lock. Any deviations from the SAP after database lock will be documented in the final Clinical Study Report (CSR).

2 STUDY OVERVIEW

2.1 Study Objectives

2.1.1 *Primary Objective*

The primary objective is to assess the interaction between ADX-629 and ethanol while exploring the safety, tolerability, and activity of ADX-629 in subjects with elevated ethanol levels.

2.2 Study Design

2.2.1 *Overview*

ADX-629-ET-001 is a Phase 1b, single-center, double-blind, placebo-controlled, randomized, crossover study to assess the interaction between ADX-629 and ethanol while exploring the safety, tolerability, and activity of ADX-629 in subjects with elevated ethanol levels. Approximately 30 subjects are expected to be enrolled in the study.

This study will utilize a 2-sequence, 2-period, 2-way crossover design. Subjects will be randomized to 1 of 2 treatment sequences (AB or BA) on Day 1 of Treatment Period 1.

- Treatment A: 3 oral doses of ADX-629 600 mg (2 × 300 mg) oral tablets; and
- Treatment B: 3 oral doses of matching placebo.

Study procedures will be completed during the following periods:

- A Screening Period (Day -28 to -2);
- Two 3-day inpatient periods (Treatment Periods 1 and 2) (from Check-In through completion of treatment period), each consisting of the following:
 - Check-In: Subjects will be admitted to the study site on the day prior to dosing in each treatment period. Baseline symptom and sign assessments (except for the Clinical Global Impression [CGI] Improvement Scale) will be completed, and subjects will then be housed overnight where they will be required to adhere to a standardized high-fat, high-sucrose diet;
 - Day 1: 1 dose of study drug will be administered at approximately 4:30pm followed by standardized ethanol consumption as outlined in the manual, and 1 dose of study drug will be administered at approximately 7 pm followed by continued standardized ethanol consumption to reach a target blood alcohol concentration (BAC) of 0.14 g/100 mL, measured via breathalyzer. For more details on the breathalyzer measurements, refer to the Study Procedures Manual. Symptom and sign assessments (with the exception of the CGI Improvement Scale) will be evaluated and should be completed as soon as practical after target BAC is reached. Study procedures will be reviewed for randomized subjects, and, based on the emerging data, the standardized ethanol solution and/or

BAC testing methods may be modified as needed to ensure target BAC is reached within a 4-hour window for the remaining subjects; and

- Day 2: 1 dose of study drug will be administered at approximately 8 am, and symptom and sign assessments (including the CGI-Improvement Scale) will be completed at approximately 7 am, 10 am, and 1 pm. Subjects will be discharged from the study site after completion of study procedures (approximately 12 hours after the last dose of study drug). Prior to discharge, vital signs will be measured. Subjects will have to achieve a BAC of 0.00 g/100 mL as measured by a breathalyzer before discharge.
- A follow-up telephone call will occur 3 days (± 1 day) after completion of Treatment Period 2.

For subjects who are withdrawn from the study prior to completion, study procedures will be performed at an Early Termination Visit.

There will be a 14-day (± 2 days) washout period between the last dose of study drug in Treatment Period 1 and the first dose of study drug in Treatment Period 2. Subjects will need to refrain from drinking alcohol during the washout period.

2.2.2 *Randomization and Blinding*

Subjects will be randomized to 1 of 2 treatment sequences (AB or BA) on Day 1 of Treatment Period 1.

- Treatment A: 3 oral doses of ADX-629 600 mg (2×300 mg) oral tablets; and
- Treatment B: 3 oral doses of matching placebo.

Subjects, Investigators, and study site personnel (including the Sponsor/designee) involved in the administration and assessment of the study drug will be blinded to the subject treatment assignments throughout the study.

2.2.3 *Study Drug*

All subjects will receive 3 doses of ADX-629 600 mg (2×300 mg) oral tablets and 3 doses of matching placebo. The study drug will be administered twice on Day 1, the first dose prior to the commencement of the standardized ethanol consumption, and once on the day following ethanol consumption (Day 2). No dose interruptions or reductions will be permitted.

2.2.4 *Sample Size Determination*

Approximately 30 subjects are expected to be enrolled in the study. The sample size is not based on statistical considerations and is not formally powered as all endpoints are exploratory in nature.

2.3 *Study Endpoints*

As this study is not formally powered and there are no adjustments for multiplicity, and since the interaction between ethanol and ADX-629 has not been previously assessed, all efficacy endpoints are exploratory.

2.3.1 *Primary Exploratory Efficacy Endpoints*

The primary exploratory efficacy endpoints include the following:

- Assessment of symptoms using the Global Impression Visual Analog Scale, Clinical Global Impression (CGI)-Impairment Severity Scale, CGI-Improvement Scale, and the Alcohol Toxicity Symptom Scale;
- Assessment of signs, determined by evaluation of the following:
 - Objective flushing and ocular redness scales (via digital photography); and
 - Proprioception tests (Romberg Test [time of up to 60 seconds], One Leg Stand Test [time of up to 60 seconds], Straight-Line Heel-to-Toe Test [up to 100 steps]).
- Assessment of ADX-629 pharmacodynamic activity, determined by evaluation of the following PD markers 1 hour after the target BAC is achieved and 1 hour after the last dose of study drug on Day 2 of each treatment period:
 - 4-hydroxynonenal (HNE), acetaldehyde, malondialdehyde-acetaldehyde adduct (MAA), and malondialdehyde (MDA) plasma concentrations; and
 - Plasma cytokine concentrations including, but not limited to, interferon gamma, IL-1b, IL-10, IL-12, and IL-17.

2.3.2 Safety Endpoints

The safety endpoints will include:

- AEs;
- Physical examinations;
- Vital signs (blood pressure, heart rate, respiratory rate, temperature, and oxygen saturation);
- 12-lead electrocardiograms (ECGs);
- BAC;
- Clinical laboratory assessments (including chemistry, hematology, and urinalysis); and
- Lipid panel evaluations.

3 STATISTICAL METHODOLOGY

3.1 General Considerations

3.1.1 Analysis Day

Analysis day will be calculated from the date of first dose of study drug. The day of the first dose of study drug will be Day 1, and the day immediately before Day 1 will be Day -1. There will be no Day 0.

3.1.2 Analysis Visits

Scheduled visits will be assigned to analysis visits as recorded on the CRF.

3.1.3 Definition of Baseline

Baseline for safety assessments is defined as the last measurement prior to the first dose of study drug.

Baseline for efficacy assessments is defined as the last measurement prior to the first dose of study drug for each study period.

3.1.4 *Summary Statistics*

In general, categorical variables will be summarized by the count and percentage of subjects. Continuous variables will be summarized by the number of non-missing observations, mean, standard deviation, median, minimum, and maximum values.

3.1.5 *Handling of Dropouts and Missing Data*

Dates for AEs and concomitant medications will be printed in a format of DDMMYY YYYY. In cases of incomplete dates for AE and concomitant medications, no imputation of start/end dates or times will be performed. If the partial AE onset date information does not indicate that the event started prior to or after the treatment, the event will be classified as treatment-emergent.

If a medication date is missing or partially missing and it cannot be determined whether it was taken prior or concomitantly, it will be considered a concomitant medication.

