- Day 1: 1 dose of study drug will be administered at approximately 4:30 pm followed by standardized ethanol consumption as outlined in the manual, and then 1 dose of study drug will be administered at approximately 7 pm followed by continued standardized ethanol consumption to reach a target blood alcohol concentration (BAC) of 0.14 g/100 mL, measured via breathalyzer. For more details on the breathalyzer measurements, refer to the Study Procedures Manual. Symptom and sign assessments (with the exception of the CGI-Improvement Scale) will be evaluated and should be completed as soon as practical after target BAC is reached. Study procedures will be reviewed for randomized subjects, and, based on the emerging data, the standardized ethanol solution and/or BAC testing methods may be modified as needed to ensure target BAC is reached within a 4-hour window for the remaining subjects; and

Note: Subjects will be observed for safety during the treatment periods by study site personnel who will be present to assist subjects at all times; there will be a minimum

requirement of at least 2 study site personnel to assist subjects during their assessments. Safety measures will be in place to prevent falling.

Note: Ethanol will be administered in a standardized oral solution. For more details on the consumption guidelines, refer to the Study Procedures Manual.

- Day 2: 1 dose of study drug will be administered at approximately 8 am, and symptom and sign assessments (including the CGI-Improvement Scale) will be completed at approximately 7 am, 10 am, and 1 pm. Subjects will be discharged from the study site after completion of study procedures (approximately 12 hours after the last dose of study drug). Prior to discharge, vital signs will be measured. Subjects will have to achieve a BAC of 0.00 g/100 mL as measured by a breathalyzer before discharge.
- A follow-up telephone call will occur 3 days (± 1 day) after completion of Treatment Period 2.

For subjects who are withdrawn from the study prior to completion, study procedures will be performed at an Early Termination Visit.

There will be at least a 14-day washout period between the last dose of study drug in Treatment Period 1 and the first dose of study drug in Treatment Period 2. Subjects will need to refrain from drinking alcohol during the washout period.

An individual subject's participation in the study is estimated to be approximately 41 days.

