8.8 Vital Signs

Vital signs will include blood pressure, heart rate, respiratory rate, temperature, and oxygen saturation. Vital signs will be measured after a minimum 5-minute rest on Day 1 before each study drug administration, and blood pressure, heart rate, and oxygen saturation will be measured approximately every 30 minutes after consumption of alcohol until the subject's BAC returns to 0.11 g/100 mL. Vital signs may be measured in the seated or supine position. If there is a clinically important change in blood pressure or body temperature from the previous recording with values outside the normal range, measurements will be repeated to confirm the change.

Prior to discharge on Day 2, vital signs will be measured (both treatment periods).

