8.9 Electrocardiograms

All 12-lead ECGs will be performed after the subject has been resting in the supine position for at least 10 minutes prior to each study drug administration on Days 1 and 2 and prior to discharge on Day 2. Repeat ECGs are permitted at the discretion of the Investigator.

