3.5 Safety Assessment

Safety data will be summarized by treatment sequence and in total based on the Safety Population.

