3.5.2 Clinical Laboratory Tests

Clinical laboratory assessments will include clinical chemistry, hematology, and urinalysis.

Continuous laboratory variables will be summarized in terms of observed values and the change from Baseline at each visit. Categorical laboratory variables will be summarized at each visit with counts and percentages of subjects.

A blood sample for lipid panel evaluation will be collected after fasting at Screening and on Day 2 of both treatment periods. Observed values and change from Baseline at each scheduled visit will be summarized.

3.5.3 *Vital Signs*

Vital signs will include blood pressure, heart rate, respiratory rate, temperature, and oxygen saturation.

Observed values and change from Baseline at each scheduled visit and timepoints will be summarized.

3.5.4 *Blood Alcohol Concentration*

Ethanol will be administered in a standardized oral solution to reach a target BAC of 0.14 g/100 mL following the first dose of study drug on Day 1.

A confirmatory blood ethanol test will be obtained on Day 1 of both treatment periods after the start of ethanol consumption but prior to the subject's final drink and associated 45-minute breathalyzer test.

All the data collected will be listed.

3.5.5 *Electrocardiograms*

Each continuous variable - heart rate (bpm), PR interval (msec), QRS duration (msec), QT interval (msec), QTcF (msec), RR interval (msec) - will be summarized in terms of observed values and changes from Baseline at each visit.

Overall interpretation (normal/ abnormal and not clinically significant/ abnormal and clinically significant) will be summarized along with the proportion of subjects with abnormal QTcF intervals in the categories below will be provided.

- Absolute QTcF interval >450 msec
- Change from baseline QTcF interval increase >30 msec

All the data collected will be listed.

3.5.6 *Physical Examinations*

A complete physical examination will be performed at Screening (and the Early Termination Visit, if applicable) and will consist of general appearance, skin, head, eyes, ears, mouth, oropharynx, neck, heart, lungs, abdomen, extremities, and neuromuscular system.

Counts and percentages of subjects with physical examination abnormalities will be summarized at each visit.

All the data collected will be listed.

3.5.7 *Other Safety Assessments*

Drug and alcohol screen, SARS-CoV-2 RNA, FSH test, Peth blood test, pregnancy testing, fibroscan, AUDIT test and CAGE questionnaire will be listed.

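### The safety baseline is set once for the whole study, so Period 2 ECG and vital-sign changes, including the QTcF >30 msec flag, are measured from a value about two weeks old

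*SAP*

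**What the plan says.** SAP 3.1.3 gives two baseline definitions, one after the other. For safety: "Baseline for safety assessments is defined as the last measurement prior to the first dose of study drug". For efficacy: "Baseline for efficacy assessments is defined as the last measurement prior to the first dose of study drug for each study period". They differ only in the period qualifier, which safety lacks.

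SAP 3.5.3 and 3.5.5 summarize changes from baseline for vital signs and ECG variables. The ECG section adds a threshold category: "Change from baseline QTcF interval increase >30 msec". Neither section restates or overrides the baseline, and SAP section 5 (changes from the protocol) does not mention it. On layout, SAP 3.5 says: "Safety data will be summarized by treatment sequence and in total based on the Safety Population".

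The protocol schedules pre-dose measurements in each period. ECGs (Protocol 8.9) are taken "prior to each study drug administration on Days 1 and 2 and prior to discharge on Day 2". For vital signs, Protocol 8.8 says: "Vital signs will be measured after a minimum 5-minute rest on Day 1 before each study drug administration". Each treatment period has its own Day 1.

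The washout is described in two ways. SAP 2.2.1: "There will be a 14-day (± 2 days) washout period". Protocol 3.1: "There will be at least a 14-day washout period".

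**The concern.** A change from baseline in a crossover is normally read as what happened after dosing in that period. With one study-level baseline, a Period 2 change also carries whatever shifted between the two admissions. The Period 2 pre-dose ECG, which is the natural reference, becomes a change value that can itself meet the QTcF >30 msec criterion.

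Because safety is tabulated by sequence, the age of the baseline is tied to treatment inside each column. In AB, ADX-629 changes have a same-period reference and placebo changes the old one. In BA it is the reverse. A reader who compares the two treatments within a sequence is comparing changes built on different references.

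The point is limited to ECG and vital signs. Lipids are drawn only at Screening and on Day 2 of each period, so neither period has a Day 1 pre-dose value. The timing of the other laboratory tests cannot be checked because the Schedule of Procedures is not shown.

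**Working it through.** The plan states no figure on this point to reproduce. The check is a reading of the definitions, timeline arithmetic, a count, and an illustration with assumed SDs.

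**1. Which baseline applies.** The period qualifier appears only in the efficacy sentence. SAP 3.1.1 also counts analysis days from a single first dose. The safety baseline is therefore one value per subject, taken before Period 1 dosing.

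**2. Age of that baseline in Period 2.** The first dose is at about 4:30 pm on Day 1 and the last dose of the period at about 8 am on Day 2, which is 15.5 h, or 0.65 days, later. Age at the first Period 2 dose = 0.65 + washout.

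| Washout (days) | Age (days) | Calendar days, Day 1 to Day 1 |
|---|---|---|
| 12 | 12.65 | 13 |
| 14 | 14.65 | 15 |
| 16 | 16.65 | 17 |

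The SAP washout gives 13 to 17 calendar days. The protocol washout gives 15 or more, with no upper limit.

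**3. Count of ECG changes per completer.** There are 3 pre-dose ECGs and 1 before discharge in each period, so 4 × 2 = 8.
- Study-level baseline: 8 − 1 = 7 changes, 3 in Period 1 and 4 in Period 2. The old reference serves 4/7 = 57%. One of the 7 (14%) precedes any Period 2 dose. In 30 subjects that is 30 of 30 × 7 = 210.
- Per-period baseline: 3 + 3 = 6 changes, all with a same-period reference.

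This assumes that every scheduled ECG yields a change value.

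**4. Could the Period 2 pre-dose ECG reflect drug?** In BA, no ADX-629 has yet been given. In AB, using the mean half-lives of 3.49 to 6.83 h in Protocol 1.1.2, a 12-day washout is 288/6.83 = 42 to 288/3.49 = 83 half-lives. A 14-day washout is 336/6.83 = 49 to 336/3.49 = 96. Residual drug is negligible in either case.

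**5. Illustration of the >30 msec flag.** The documents give no QTcF SD. Assume no drug effect, no drift and normal changes.
- Same-period reference, change SD 15 msec: P(change > 30) = P(Z > 2.00) = 2.3%; × 30 = 0.68 flags per ECG timepoint.
- Old reference, with an independent between-period SD s added at each occasion: SD = √(15² + 2s²).
  - s = 0: SD 15, 2.3%, 0.68 flags.
  - s = 8: SD = √353 = 18.8, P(Z > 1.60) = 5.5%, 1.65 flags.

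The ratio runs from 1.0 to 0.0552/0.0228 = 2.4.

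A separate simulation (400,000 subjects per setting) used other assumed values: between-period SD 4 to 12 msec, within-period SD 6 to 10 msec, no drug effect, no drift. It looked at the chance of at least one Period 2 flag per subject. This was 0.6% to 17.4% with the study-level baseline (4 ECGs) and 0.05% to 4.4% with a per-period baseline (3 ECGs). The Period 2 pre-dose ECG alone met the criterion in 0.2% to 8.8% of subjects. These figures use a different measure and do not confirm the first set, but the direction is the same.

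**6. What cancels.** With common baseline b, (Period 2 − b) − (Period 1 − b) = Period 2 − Period 1, so b drops out of a paired difference. It does not drop out of a single-period change summary or a threshold count, and those are what SAP 3.5.5 describes.

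**The case against.** The best defence is that this is a deliberate convention. The two definitions sit side by side, and the same study-level first dose anchors analysis day, concomitant medication and treatment-emergent events. The protocol promises no period-specific safety baseline. A study-level reference also shows whether a subject returned to the pre-study value, whereas a per-period baseline would absorb a persistent Period 1 shift. That use is legitimate and can be kept as a supplementary summary. It is a weak reason to make it the only reference, because a washout of at least 42 half-lives leaves little drug effect to carry forward.

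Several limits on the harm stand. Output is descriptive in an unpowered, exploratory study. Observed values are summarized and all ECG data listed, so same-period changes could be derived later. The QTcF >450 msec category needs no baseline. With sequences of similar size, extra flags fall equally on both treatments in expectation.

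It is also fair that the SAP does not say which ECGs feed the >30 msec category: ECG changes are described by visit, vital signs by visit and timepoint. The separate programming specifications might narrow the set. So the count of 7 is conditional, but the definition that makes the Period 2 pre-dose ECG post-baseline is not.

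Finally, a per-period baseline does not separate treatment from period within a sequence. Nor does it separate drug from ethanol, since every later ECG in a period follows the start of drinking. It removes only the between-period component.

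**Conclusion.** The point holds on the text. The safety baseline is a single pre-Period 1 value, Period 2 ECG and vital-sign changes rest on it some 13 to 17 days later (15 or more under the protocol's washout), and the Period 2 pre-dose ECG is post-baseline by definition. None of this depends on assumed variability.

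The effect is extra noise in Period 2 changes and flags, and references of unequal age within each sequence column. It is not a directional bias overall. Its size is uncertain: under the assumed SDs it runs from no increase to about 2.4 times as many chance flags per ECG, or at most about one extra flag per timepoint in 30 subjects (1.65 − 0.68 = 0.97). The impact is minor to moderate. The change should be made because it is cheap and the needed measurements are already planned.

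**What to change.** Replace the safety sentence in SAP 3.1.3 with two:

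> *For ECG, vital signs and any other safety assessment with a pre-dose value collected within the treatment period, baseline is the latest value obtained from that period's Check-In up to its first dose. Where none is collected (for example lipids), baseline is the latest value before dosing starts in Treatment Period 1.*

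State in SAP 3.5.5 which ECGs enter the >30 msec category. If a check on return to the pre-study level is wanted, keep the study-level baseline as a labelled supplementary summary.

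The washout wording in SAP 2.2.1 and Protocol 3.1 must also be reconciled. That is a separate inconsistency, which matters here only because it sets the age of the baseline.

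The cost is a short SAP edit and minor programming, with no new assessments. The optional supplementary summary would add one further table set.
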